8.4 Unscheduled Visits

Additional (unscheduled) visits will be performed and recorded as required for the optimal treatment and follow-up of the subject. The tests, exams, and

procedures required at the unscheduled visit are dependent upon the reason for the unscheduled visit and will be performed at the investigator's discretion. The following tests, exams, and procedures may be conducted at the unscheduled visit:

- Review of Adverse Events and Assessment of Device Complications
- Review of Concomitant Systemic Medications
- Review of Concomitant Glaucoma Medications
- Review of Other Concomitant Ocular Medications
- Manifest Refraction and Snellen Visual Acuity
- Intraocular Pressure
 - Intraocular Pressure will be measured utilizing Goldmann applanation tonometry. Two consecutive measurements will be obtained. The intraocular pressure should be performed at the same time of day at all visits, when possible.
- Slit Lamp Examination
- Gonioscopy
- Funduscopy Examination
- Ultrasound biomicroscopy or Anterior Segment Optical Coherence Tomography to measure the capsule thickness around the plates (Months 6 and 12 only)

8.5 Early Withdrawal

All subjects have the right to withdraw from the study at any point. The site investigator or the Medical Monitor may discontinue a subject from the study for any of the following reasons:

- a. Noncompliance with the study requirements
- b. At the discretion of the Investigator or Medical Monitor, due to subject safety concerns.

If a subject withdraws prematurely from the study, a genuine effort must be made to determine the reason(s) for the subject's early discontinuation and the subject should complete an Early Withdrawal visit, which includes the

same tests, exams, and procedures required at the Month 12 Post-Operative Visit.

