5.1 Primary Endpoint

The primary endpoint is the mean intraocular pressure in the porous plate group as compared to the silicone plate group at 12 months.

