5.2 Secondary Endpoints

- (a) The mean number of anti-glaucoma medications in the porous plate group as compared to the silicone plate group at 12 months.
- (b) Surgical success in the porous plate group as compared to the silicone plate group at 12 months. Surgical success is defined as:

Unqualified surgical success: 5 mmHg < intraocular pressure < 22 mmHg with no loss of light perception and no additional glaucoma procedures or glaucoma medications.

Qualified surgical success: 5 mmHg < intraocular pressure < 22 mmHg with no loss of light perception and no additional glaucoma procedures, but with the adjunctive use of glaucoma medications.

6. Study Synopsis

Title:	Comparison of Silicone and Porous Plate Ahmed Glaucoma Valves
Study Period:	12 months, 9 visits: Screening/Baseline; Day of Surgery; Post-Operative Days 1 and 7; and Post-Operative Months 1, 3, 6, 9, and 12. Unscheduled visits will be performed and recorded as required for the optimal treatment and follow up of the subject.
Study design:	A prospective, two-arm, unmasked, randomized, controlled study.
Objectives:	A prospective, randomized trial to evaluate and compare the clinical outcomes after implantation of the porous plate (polyethylene) with the silicone plate Ahmed Glaucoma Valve in subjects with intractable glaucoma.
Control Arm:	Subjects undergoing surgery with the silicone plate Ahmed Glaucoma Valve (Model FP7)
Treatment Arm:	Subjects undergoing surgery with the porous plate Ahmed Glaucoma Valve (Model M4)
Subject Population:	Patients with intractable glaucoma who are candidates for valve surgery.
Sample Size:	Total of 88 subjects with a planned 40 subjects in each arm. Each site can enroll a maximum of 40 subjects.
Follow-up duration:	12 months.

7. Study Population

This is a prospective, two-arm, unmasked, randomized, controlled study of 80 enrolled subjects with intractable glaucoma that have not responded to conventional medical and surgical therapy. The study will accrue up to 88 subjects to allow for a dropout rate of 10 %.

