9.4 Device Explant, Repositioning, or Replacement

The device may be revised, repositioned, removed, or replaced by the same kind of device or another marked drainage device if the original device was damaged or determined to be not functioning. If surgical intervention for repositioning or replacement is required, the subject will be required at a minimum to complete all of the protocol required post-operative visits. If sequelae persist, the subject should be followed until all sequelae are considered to be stabilized or resolved.

10. Safety

At each visit, the ocular health of the subject will be assessed. The cornea, anterior chamber, trabecular meshwork, device implant location (if available), and fundus will be examined. Any ocular unanticipated adverse events occurring during the study whether they are considered to be device related or not, must be documented on the Adverse Event Case Report Form. Date and time of the event, event severity, treatment (if any), and the assessed relationship of the event to the study devices will be recorded on the Adverse Event Case Report Form. Conditions that exist at the time the subject is enrolled in the study do not need to be recorded on the Adverse Event Form as adverse events, unless they increase in severity during the study and constitute an unanticipated adverse event..

The collection and recording of unanticipated adverse events will begin at the start of the surgical intervention and will end at the subject's Month 12 or Early Termination Visit. Unanticipated adverse events must be followed until the adverse event has recovered or recovered with ongoing sequelae that will likely not change in the view of the investigator. This period *may* extend beyond study termination.

A brief overview of the differences between anticipated, unanticipated and serious adverse events is provided.

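### Section 8.5 lets the unmasked investigator or the Medical Monitor discontinue an implanted subject from the study, and nothing then asks for the 12-month intraocular pressure that is the primary endpoint

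*Combined protocol and SAP*

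**What the plan says.** Section 8.5 (Early Withdrawal) states: "The site investigator or the Medical Monitor may discontinue a subject from the study for any of the following reasons". Ground (a) is "Noncompliance with the study requirements", with no definition or threshold. Ground (b) is "At the discretion of the Investigator or Medical Monitor, due to subject safety concerns", with no criteria. The same section provides for an exit assessment: "the subject should complete an Early Withdrawal visit, which includes the" Month 12 tests. It mentions no visit after that one.

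The surrounding text on this point:

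- The synopsis (Section 6) describes the trial as "A prospective, two-arm, unmasked, randomized, controlled study".
- Section 5.1: "The primary endpoint is the mean intraocular pressure in the porous plate group as compared to the silicone plate group at 12 months".
- Section 9.4, on repositioning or replacement of the device: "the subject will be required at a minimum to complete all of the protocol required post-operative visits".
- Section 10: recording of unanticipated adverse events "will end at the subject's Month 12 or Early Termination Visit". Events already open are followed until recovered or stable, if need be beyond the end of the study (also Section 10.6).
- Section 11.6 puts every operated subject in the primary analysis, says that subjects are monitored to the end of the study period, and has treatment failures entered in the database.
- Section 11.1 expects no more than 10% of randomized subjects to miss completion of the 12 months.

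**The concern.** Rules for taking subjects out of a study usually protect them by stopping a study treatment. Here the treatment is one implantation on Day 0. Afterwards, participation consists of examinations and reviews (8.3), glaucoma and post-operative medication is at the investigator's discretion (9.2, 9.3), no medication is prohibited (9.1), and the device may be revised, removed or replaced within the study (9.4). The clinical latitude therefore already exists inside the study. For an implanted subject, discontinuation mainly removes the remaining scheduled outcome data.

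Removal for a safety concern is likely to be related to outcome, and the site investigator who may decide it knows which plate was implanted. If such removals fell unevenly on the two arms, three results could be affected:

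- the difference in mean IOP at 12 months;
- the Kaplan-Meier comparison of success (11.3), where censoring discontinued eyes would be informative;
- the comparison of complications, for those arising after exit.

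**Working it through.** **Step 1. Does any passage secure the Month 12 IOP after discontinuation under 8.5?**

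- *Early Withdrawal visit (8.5; shared Month 12 / early termination column in 8.6).* It captures IOP and adverse events at exit. It is worded as something the subject should do, and it takes place at exit rather than at Month 12. No passage says whether the exit IOP stands in for the Month 12 value.
- *Section 9.4.* It requires all post-operative visits when a device is repositioned or replaced. Its follow-up sentence names neither an eye whose device is removed without replacement nor a poorly controlled eye without reoperation. Section 8.5 contains no exception for 9.4 eyes.
- *Section 11.6.* Its statements on monitoring and on the analysis population are general. Neither limits 8.5, and no passage gives a rule for a missing 12-month IOP.

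The answer is no. A discontinued eye can lack the primary endpoint although 11.6 includes it in the analysis.

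**Step 2. Inputs for the size.**

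- From Section 11.1: 40 per arm, SD 3 mmHg, target difference 1.5 mmHg, non-completion up to 10%. For one arm, 0.10 × 40 = 4 eyes. This bound covers non-completion from every cause, not only removal under 8.5.
- Assumed, because the documents do not say: normally distributed IOP, no true difference between arms, completers compared by a two-sample t-test at two-sided 0.05, and a worst case in which only the highest-IOP eyes of one arm are lost.

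The plan's own power figure does not reproduce: 40 per arm, 1.5 mmHg and SD 3 give about 0.60 (noncentral t, two-sided 0.05), not 0.80. That is a separate matter. Here the 1.5 mmHg serves only as a yardstick.

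**Step 3. Shift in the observed mean.** Dropping the k highest of n = 40 values changes the expected mean by

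shift = -SD × (sum of the k largest expected standard normal order statistics) / (n - k).

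For n = 40 the four largest are 2.161, 1.753, 1.517 and 1.344.

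- k = 2: -3 × 3.914 / 38 = -0.309 mmHg; 0.309 / 1.5 = 21% of the target.
- k = 4: -3 × 6.775 / 36 = -0.565 mmHg; 0.565 / 1.5 = 38% of the target.

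A simulation of 40,000 trials agrees (-0.309 and -0.567 mmHg). It puts the type I error at about 8% for 2 eyes and 15% for 4, against 5% with no loss.

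**Step 4. The benign case.** If losses are random or balanced between arms, there is little bias and the cost is mainly power: about 0.55 at 36 per arm against 0.60 at 40.

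**The case against.** The strongest reply is that the protocol contains more protection than 8.5 alone suggests. Four stronger readings are tempting, and the documents support none of them.

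1. *A reader might infer that discontinuation ends all data on the eye.* It does not. The exit visit should record IOP and complications, open unanticipated events are still followed (Sections 10 and 10.6), and failures before exit are documented (11.6) and can count as events in the success analysis. What is lost is the 12-month value and anything that arises after exit.
2. *A reader might infer that 8.5 and 9.4 flatly contradict each other.* They can be read together, with 9.4 as the specific rule for repositioned or replaced devices. The text does not say so, however, and other eyes doing badly fall outside 9.4.
3. *A reader might infer that badly performing eyes will be removed.* Poor IOP control is not a listed ground. Section 8.5 also has a legitimate use before surgery, since screening may precede it by up to 60 days. The documents establish the opportunity, not the intent or the likelihood.
4. *A reader might infer a much larger bias by picturing lost eyes at 30-35 mmHg in an arm averaging 15.* Two such eyes would give 2 × 15/40 = 0.75 to 2 × 20/40 = 1.0 mmHg. Under the plan's SD of 3 they lie 15/3 = 5 to 20/3 = 6.7 SD above that mean, so the example does not fit the plan's own assumptions.

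It is also fair to say that discretion over safety should not be abolished. The gap that remains is narrow: after discontinuation, nothing asks for the Month 12 outcome.

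**Conclusion.** The point holds in this limited form. As written, 8.5 allows an implanted subject to leave scheduled follow-up by decision of the unmasked investigator or the Medical Monitor, on undefined grounds, with no request for the primary endpoint. Sections 9.4 and 11.6 reduce the gap without closing it.

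Under the worst-case assumptions above, the bias in one arm's mean is about 0.31 mmHg for 2 lost eyes and 0.57 mmHg for 4. That could distort the comparison, but it is well short of the full target difference. It rests on one-sided loss of the highest eyes only, and would largely vanish if losses were random or balanced. The change is worth making because an observed Month 12 value is better than any later handling of a missing one.

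**What to change.** Add a paragraph to 8.5. For implanted subjects, discontinuation by the investigator or the Medical Monitor does not end outcome collection. Unless the subject withdraws consent, the remaining scheduled visits are still sought, in addition to the exit visit. At minimum, the Month 12 assessment of IOP, glaucoma medications, success and adverse events is sought.

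Reconcile 8.5 with 9.4 and 11.6 on this point, including eyes whose device is removed without replacement. The change concerns data collection only. It leaves clinical and safety decisions, and the subject's right to withdraw, unchanged.

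The cost is one paragraph and no new procedure, since the visits are already planned. The downside is that sites must keep contacting poorly compliant subjects.

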8.6 Schedule of Visit Tests and Procedures

	SCR ²	Day 0	POD 1	POD 7	Mo 1	Mo 3	Mo 6	Mo 9	Mo 12/ Early Term	Un- sched Visit
Informed Consent	X									
Inclusion/ Exclusion Criteria Review	X									
Demographic Information	X									
Glaucoma Diagnosis	X									
Review of Medical & Ocular Surgical History	X									
Review of Concomitant Systemic Medications	X									
Review of Concomitant Glaucoma Medications	X									
Review of History of Previous Glaucoma Surgeries	X									
Review of Other Concomitant Ocular Medications	X									
Manifest Refraction & Snellen Visual Acuity	X		X	X	X	X	X	X	X	X ³
Intraocular Pressure	X		X	X	X	X	X	X	X	X ³
Slit Lamp Examination	X		X	X	X	X	X	X	X	X ³
Gonioscopy	X					X	X	X	X	X ³
Funduscopy Examination	X		X	X	X	X	X	X	X	X ³
Visual Field Test	X									
Study Eye Determination	X									
Pre-operative tests (labwork, EKG, physical exam) ¹	X									
Randomization		X								
Surgical Intervention		X								
Concomitant Medication Review			X	X	X	X	X	X	X	X ³
Adverse Event Review			X	X	X	X	X	X	X	X ³
Ultrasound Biomicroscopy or Anterior Segment OCT ³							X	X	X	X ³

1. A serum or urine pregnancy test is required for women of child-bearing potential only, prior to randomization.
2. All Screening Exams must be completed within 60 days of the planned Surgical Intervention, except the visual field test which must be completed within 12 months of the planned Surgical Intervention.
3. Optional.

9. Concomitant Medications and Procedures

9.1 Prohibited Concomitant Medications

There are no prohibited concomitant ocular or non-ocular medications during participation in this study.

9.2 Glaucoma Medication Management

Use of topical or systemic glaucoma medications will be documented at baseline and throughout the post-operative follow-up period for the study eye. Glaucoma medications for the study eye should be suspended only on the day of surgery and reinstated, if indicated, with necessary adjustments after surgery to manage any elevated intraocular pressure in the study eye. The decision to re-institute glaucoma medications in the study eye will be made at the discretion of the investigator.

9.3 Post-operative Medications

Selection, dosage, and frequency of the study eye post-operative topical antibiotic agent and post-operative anti-inflammatory agent will be made at the discretion of the investigator. All prescribed post-operative ocular medications must be recorded in the study records.

9.4 Device Explant, Repositioning, or Replacement

The device may be revised, repositioned, removed, or replaced by the same kind of device or another marked drainage device if the original device was damaged or determined to be not functioning. If surgical intervention for repositioning or replacement is required, the subject will be required at a minimum to complete all of the protocol required post-operative visits. If sequelae persist, the subject should be followed until all sequelae are considered to be stabilized or resolved.

10. Safety

At each visit, the ocular health of the subject will be assessed. The cornea, anterior chamber, trabecular meshwork, device implant location (if available), and fundus will be examined. Any ocular unanticipated adverse events occurring during the study whether they are considered to be device related or not, must be documented on the Adverse Event Case Report Form. Date and time of the event, event severity, treatment (if any), and the assessed relationship of the event to the study devices will be recorded on the Adverse Event Case Report Form. Conditions that exist at the time the subject is enrolled in the study do not need to be recorded on the Adverse Event Form as adverse events, unless they increase in severity during the study and constitute an unanticipated adverse event..

The collection and recording of unanticipated adverse events will begin at the start of the surgical intervention and will end at the subject's Month 12 or Early Termination Visit. Unanticipated adverse events must be followed until the adverse event has recovered or recovered with ongoing sequelae that will likely not change in the view of the investigator. This period *may* extend beyond study termination.

A brief overview of the differences between anticipated, unanticipated and serious adverse events is provided.

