10.1 Anticipated Adverse Events

Anticipated adverse events include those that might reasonably be expected to occur in this study because they are associated with glaucoma surgical procedures. Anticipated adverse events for both the porous plate and silicone plate glaucoma valves include:

- * Wound Leak
- * Shallow Anterior Chamber

- * Flat Anterior Chamber
- * Choroidal effusion
- * Exposure of Tube, Patch Graft, Plate
- * Severe Inflammation
- * Tube and/or Flow Obstruction
- * Corneal Edema
- * Motility Disturbance (i.e. Diplopia)
- * Suprachoroidal hemorrhage
- * Hypotony (≤ 5 mmHg)
- * Elevated intraocular pressure
- * Retinal Detachment

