10.2 Unanticipated Adverse Events

Unanticipated adverse events include any serious adverse effects on health or safety or any life-threatening problem or death caused by or likely directly related to the Ahmed Glaucoma Valve (M4 or FP7) or the placement of the Ahmed Glaucoma Valve (M4 or FP7) within the eye that are not typically associated with glaucoma surgical procedures.

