10.4 Assessment of Adverse Event Severity

The investigator will make an assessment of event severity for each unanticipated adverse event and serious adverse event reported during the study according to the following definitions:

Mild: An event that is easily tolerated by the subject, causing minimal discomfort and not interfering with everyday activities.

Moderate: An event that is sufficiently discomforting to interfere with the subject's normal everyday activities.

Severe: An event that prevents the subject's normal everyday activities.

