11.5 Plans for Interim Analysis

There will be no formal interim analysis. However, for purposes of safety and surgical failures only, unanticipated adverse events will be reviewed periodically by the Medical Monitor to detect a statistically significant increase of vision-threatening complications (e.g., suprachoroidal hemorrhage, endophthalmitis, and surgical failures). If vision-threatening complications and surgical failures exceed a threshold of 30% during the study, consideration will be given by the Medical Monitor to terminate the study early.

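### Section 10 records unanticipated events whether or not device related, but Section 10.2 defines them as serious and device caused, leaving non-serious atypical ocular events without an assured form or review

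*Combined protocol and SAP*

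**What the plan says.** All references are to the combined protocol and SAP.

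- **Section 10, Safety (recording rule).** "Any ocular unanticipated adverse events occurring during the study whether they are considered to be device related or not, must be documented". The rule concerns the Adverse Event form. The same paragraph makes relatedness a data item: "the assessed relationship of the event to the study devices will be recorded on the Adverse Event Case Report Form".
- **Section 10.1 (anticipated).** "Anticipated adverse events include those that might reasonably be expected to occur in this study because they are associated with glaucoma surgical procedures". Thirteen examples follow, suprachoroidal hemorrhage among them.
- **Section 10.2 (unanticipated).** "Unanticipated adverse events include any serious adverse effects on health or safety or any life-threatening problem or death", with the further conditions that they be "caused by or likely directly related to the Ahmed Glaucoma Valve (M4 or FP7) or the placement of the Ahmed Glaucoma Valve" and not be typical of glaucoma surgery.
- **Section 10.3 (serious).** Defined by hospitalization, surgical intervention, threat to sight or life, death, or significant disability. Neither relatedness nor expectedness is a condition.
- **Section 10.4 (severity).** "The investigator will make an assessment of event severity for each unanticipated adverse event and serious adverse event reported during the study".
- **Sections 10.5 to 10.7, 11.5 and 11.7 (use of the term).** The Adverse Event form, the follow-up duty and the Medical Monitor's continuous and termination reviews are all stated for unanticipated events. For the periodic review, 11.5 says "unanticipated adverse events will be reviewed periodically by the Medical Monitor".
- **Section 10.5 (serious route).** Every serious event goes on its own form and to the Medical Monitor within 24 hours.
- **Sections 11.3 and 11.6 (analysis).** Complications are compared between arms, and adverse events are tabulated by type and severity.

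**The concern.** The protocol uses one word, unanticipated, with two meanings. If relatedness is part of the definition, as in 10.2, an unrelated unanticipated event cannot exist, and Section 10's instruction to record such events has nothing to act on. A site has to choose a reading, and the protocol gives no rule for choosing.

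The choice has consequences because the word decides which events reach the Adverse Event form and which reach the Medical Monitor. The trial is unmasked and has several sites (the synopsis caps enrolment per site). Sites could therefore record the same kind of event differently. Where a site lets attribution decide, the person attributing knows which device was implanted. The introduction says the porous plate is FDA approved but has not been studied in clinical trials, so events outside the usual surgical profile are part of what this comparison should pick up.

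**Working it through.** The documents give no figure to reproduce. The check is to set the passages side by side and then follow each kind of event through the recording and review routes.

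**Step 1: relatedness.** Section 10 says relatedness does not decide whether an ocular event is recorded; it is assessed and entered on the form. Section 10.2 makes causation by the valve or its placement part of the description. These conflict directly.

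**Step 2: seriousness.** Section 10.2 speaks of serious effects, life-threatening problems and death. Section 10 lifts the relatedness condition but is silent on seriousness. A site that follows Section 10 on relatedness and looks to 10.2 for the meaning of the term could still omit non-serious events.

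**Step 3: what depends on the term.** The Adverse Event form (10.5), the collection window and the rule for pre-existing conditions (Section 10), follow-up (10.6), continuous review (10.7), periodic review (11.5) and termination review (11.7).

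**Step 4: four kinds of event, with 10.2 read literally.**

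1. *Serious, device related, atypical.* Fits 10.2. Recorded and reviewed.
2. *Serious, not attributed to the device.* Outside 10.2, so outside the Adverse Event form and the aggregate review. It still goes on the Serious Adverse Event form and to the Medical Monitor within 24 hours (10.5), so it is not lost.
3. *Non-serious, of an anticipated kind.* The investigator must identify and collect it (10.5), and it can enter the complication comparison in 11.3. No form is named, and it is outside the Medical Monitor's review.
4. *Non-serious, ocular, not typical of glaucoma surgery.* Not anticipated under 10.1, not unanticipated under 10.2, not serious under 10.3. No form is required and no review covers it. This holds whether or not it is judged device related.

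Only the fourth kind has no assured route into the database.

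**Step 5: scope of the 11.5 review.** It covers unanticipated events, yet its stated purpose is to detect an increase in vision-threatening complications, with suprachoroidal hemorrhage as an example. Section 10.1 lists that event as anticipated. As worded, the review excludes an event it is meant to detect. A sight-threatening case would reach the Medical Monitor individually through the serious route, but it is not within the stated scope of the periodic review.

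**The case against.** The strongest reply is that 10.2 is not a closed definition. It says that unanticipated events include certain effects, and Section 10 introduces 10.1 to 10.3 as a brief overview. Section 10.4 names unanticipated and serious events separately, which suggests the first is not simply a subset of the second. A site that obeys Section 10 would record unrelated ocular events. Adverse events and device complications are also reviewed at every post-operative visit, all adverse events go to the IRB under site guidelines, the 11.6 tabulation is not restricted to unanticipated events, and 10.1 is worded generally enough to take in many unlisted post-surgical events. A Manual of Procedures, not available here, may say more.

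Much of this stands. It makes the loss conditional on how a site reads 10.2, and it narrows the affected class. It does not remove the conflict: two readings remain open, and a visit review or an IRB report does not name a study form.

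Three stronger readings are tempting and are not supported.

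- A reader might infer that events not attributed to the device drop out in general. Section 10.5 rules this out for serious events.
- A reader might take the mild grade in 10.4 as a further contradiction of a serious-only definition. Severity in 10.4 concerns interference with daily activities, while seriousness in 10.3 concerns outcomes such as hospitalization, surgery or threat to sight. An event can be serious and graded mild.
- A reader might want a numerical size for the bias between arms. The documents give no rate of atypical events and no attribution rates, so any such figure would be invented.

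**Conclusion.** The conflict between Section 10 and Section 10.2 is real and should be reconciled. Its consequence is limited to one class: non-serious ocular events not typical of glaucoma surgery, which a site following 10.2 would neither have to put on a form nor submit to review. Their capture could differ by site, because sites may read the term differently, and by arm, because judgments about events are made by people who know the device. That is a possibility created by the wording; the documents do not show that it would happen or how large it would be.

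The conclusion assumes that at least some sites treat 10.2 as the operative definition and that the unseen manual does not override it. The mismatch between the 11.5 review and 10.1 needs neither assumption about how sites act, since it lies in the listed events themselves. Neither issue touches the primary comparison of intraocular pressure; both affect the completeness of the safety data and its monitoring.

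**What to change.** 1. In 10.2, define an unanticipated adverse event as any ocular adverse event that is not anticipated under 10.1, meaning neither listed there nor otherwise expected with glaucoma surgery, regardless of seriousness or relatedness. Keep the general criterion of 10.1; treating its list as closed would turn expected but unlisted events into unanticipated ones.
2. Record seriousness, severity and relatedness as separate fields, so that none of them decides whether an event is entered.
3. Keep the present 10.2 wording as the definition of a subset, for example 'unanticipated adverse device effect'. That wording is not confined to ocular events, so its breadth should be preserved.
4. Align the scope of the 11.5 review with its stated purpose, so that the events it is meant to detect, including suprachoroidal hemorrhage, are among those reviewed.

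The cost is protocol wording plus a few more Adverse Event forms and follow-up entries per site. No assessment is added, because adverse events are already reviewed at each post-operative visit.
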